Name of sponsor company: HighTide BioPharma Pty. Ltd.

Name of finished product: HTD1801 Tablets

Name(s) of active ingredient(s): Berberine Ursodeoxycholate (HTD1801)

Analysis of Primary Endpoint:

The primary endpoint is absolute change from Baseline to Week 18 in LFC, or absolute change from Baseline to the Early Termination (ET) visit for subjects who terminate the study prematurely. Absolute change from Baseline in LFC will be assessed by analysis of covariance that includes the effects of treatment group, Baseline LFC, and Baseline ALT. Comparison of each active treatment group to placebo will be tested at the 5% level of significance without adjustment for multiple tests. Secondarily, comparison of the 2 active treatment groups with each other will be tested at the 5% level.

Analysis of Secondary Endpoints:

Relative (percent) change from Baseline in LFC will be analyzed by the same model described for the primary endpoint. Normalization of LFC will be analyzed by logistic regression that includes the effects of treatment group, Baseline LFC, and Baseline ALT.

All additional secondary endpoints are continuous and each will be assessed by analysis of covariance that includes treatment group and the Baseline value of the analysis variable. All secondary analyses (except LFC) will have missing Week 18 values imputed using a multiple imputation procedure for all subjects with an available measurement prior to Week 18.

Safety Evaluation

Safety Endpoints:

Adverse events and changes in physical examination, vital signs, electrocardiogram (ECG), and clinical laboratory values will be used to evaluate safety and tolerability. Adverse event incidence will be assessed during the Double-Blind Treatment Period. Adverse event type, relationship, severity, onset, and duration will be presented by treatment group within the Double-Blind Treatment Period.

Safety Analysis:

Changes in physical examination, vital signs, ECG, and clinical laboratory values will be presented using summary statistics. Numbers and percentages of the first occurrence for each adverse event will be presented.

Sample Size:

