3.4.2 Safety

Adverse events and changes in physical examination, vital signs, electrocardiogram (ECG), and clinical laboratory values will be used to evaluate safety and tolerability. Adverse event incidence will be determined during the Double-Blind Treatment Period. Adverse event type, relationship, severity, onset, and duration will be presented by treatment group within the Double-Blind Treatment Period.

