6.3.5 Adverse Events

Adverse events will be collected from the time at which the potential subject signs the ICF. Subjects will be instructed to report all AEs during the study and will be assessed for the occurrence of AEs throughout the study until at least 30 days after discontinuing the study drug. General and non-leading questions such as "How are you feeling?" should be asked when assessing the occurrence of AEs. The definition, reporting, and recording requirements for AEs are described in Section 7.0.

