9.2.5 Safety Analysis

The safety dataset will be used for all safety analyses. Safety analyses will address AEs, physical examinations, vital signs, ECGs, and clinical laboratory assessments.

Adverse event type will be coded using MedDRA. Adverse event data will be listed individually; AE incidence will be summarized by system organ class and preferred terms within a system organ class for each treatment group. Adverse event type, relationship, severity, onset, and duration will be presented by treatment group within the Double-Blind Treatment Period. Liver-specific AEs also will be included.

The number of subjects with AEs, as well as the number of AEs, also will be displayed. At the subject-level, each AE will be counted only once for a given subject within a specified system organ class, preferred term. If the same AE occurs on multiple occasions for a subject, the occurrence with the highest severity and relationship to study medication will be reported. Individual AE terms will be reported as separate events.

Changes in vital signs, ECGs, and clinical laboratory parameters from Baseline to end of study will be examined and displayed using shift tables (low, normal, high). Shift tables for Week 18, or the last available study visit, will be presented relative to Baseline for all clinical laboratory parameters.

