3.3.7. Definitions and Terminology

Age

The age of a subject is defined as the number of whole years between the subject's birth date and the treatment start date.

Day 0 (Baseline)

Day 0 is the earliest day that study drug is initiated.

Study Day

Study Day is defined relative to Baseline (Day 0). Thus, the study day of an event is calculated as:
$$\text{Study Day} = \text{event date} - \text{date of Day 0}.$$

Study Visit

Study Visit is the nominal visit as recorded on the CRF.

Days on Treatment

Days on Treatment is calculated as Final Day on Treatment based on the End of Study eCRF page – First Day on Study Treatment + 1.

Baseline Value

For purposes of analysis, the baseline value is defined as the last non-missing value obtained prior to initiation of study drug.

Change from Baseline

Change from baseline for a given endpoint is defined as the Study Day X value minus the Baseline Value.

Percent (Relative) Change from Baseline

Percent, or relative, change from Baseline for a given endpoint is defined as the change from Baseline at Study Day X divided by the Baseline value, multiplied by 100 $((\text{CFB}/\text{BASE}) \times 100)$.

Adverse Event

An AE is defined as any untoward medical occurrence associated with the use of a drug in humans, whether or not considered drug related. An AE can be any unfavorable and unintended sign (including an abnormal laboratory finding), symptom, or disease (new or exacerbated) temporally associated with the use of the investigational product, regardless of whether it is considered to be related to the investigational product. All AEs will be recorded on the Adverse Event CRF.

Treatment-emergent Adverse Event

A TEAE will be an AE that occurred during the study after the first dose of study drug or that was present prior to dosing and exacerbates after the first dose of study drug. Additionally, it is assumed that an Adverse Event which was reported to have started on Day 1 without an associated onset time occurred after the initiation of study drug.

Concomitant Medications

Concomitant medications are those medications taken on or after the initiation of study drug. This definition includes medications started prior to the initiation of study drug, but continuing concomitantly with study drug.

Prior Medications

Prior medications are those medications taken prior to the initiation of study drug.

Total Bile Acid

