5.3. SAFETY

5.3.1. Adverse Events

AEs will be mapped to a Medical Dictionary for Regulatory Activities (MedDRA) version 20.1 preferred term (PT) and system organ classification (SOC). If a subject experiences multiple events that map to a single preferred term, the greatest severity grade according to the Common Terminology Criteria for Adverse Events (CTCAE) Version 4.0, and strongest investigator assessment of relation to study medication will be assigned to the preferred term for the appropriate summaries. Should an event have a missing severity or relationship, it will be classified as having the highest severity and/or strongest relationship to study medication. The occurrence of TEAEs will be summarized by treatment group by SOC, PT, and severity. Separate summaries of treatment-emergent serious adverse events (SAEs), TEAEs related to study drug, severe or life-threatening TEAEs, and TEAEs leading to the discontinuation of study treatment will be generated. Additionally, the occurrence of liver-specific AEs will be summarized by treatment group. All adverse events reported will be listed for individual subjects showing verbatim term, PT and SOC. All AEs that occurred prior to the initiation of study treatment will be excluded from the tables but will be included in the listings.

Missing onset dates will be imputed as previously outlined in Section 3.3.5 as required to determine treatment-emergent events.

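### The SAP's adverse event tables run through the off-drug follow-up contact, while the protocol places adverse event incidence within the Double-Blind Treatment Period, and no treatment-period table is planned

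*SAP*

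**What the plan says.** **Protocol.** The synopsis (Safety Endpoints) states: "Adverse event incidence will be assessed during the Double-Blind Treatment Period". Section 3.4.2 repeats this: "Adverse event incidence will be determined during the Double-Blind Treatment Period". Section 9.2.5 says that AE type, relationship, severity, onset and duration "will be presented by treatment group within the Double-Blind Treatment Period". Collection runs longer than that: under section 6.3.5, subjects are assessed for AEs "throughout the study until at least 30 days after discontinuing the study drug". Section 5.1.6 requires a follow-up contact at least 30 days after the last dose and discharges the subject from the study only after it. Table 1 puts Week 18 at Day 126 and the follow-up at +30 days with a +7 day window.

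**SAP.** Section 3.3.7 defines the TEAE: "A TEAE will be an AE that occurred during the study after the first dose of study drug", or one present before dosing that worsens afterwards. Neither limb has an end relative to last dose. Section 5.3.1 states the only timing exclusion: "All AEs that occurred prior to the initiation of study treatment will be excluded from the tables". The AE tables listed in section 10 (14.3.1.1 to 14.3.1.5) are all TEAE tables on the Safety Set, and none is restricted to the treatment period.

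**The concern.** The two documents stop counting AEs at different times. A subject remains in the study until the follow-up contact is complete, so an event that starts during follow-up meets the SAP definition of a TEAE. It lies outside the period that the protocol names for AE incidence.

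Safety and tolerability is a stated secondary objective, and the TEAE tables are how the two doses will be compared with placebo. If on-drug and off-drug events are pooled in one count, a reader cannot tell whether post-treatment events hide a signal or inflate it. The mix of on-drug and off-drug time also differs between subjects who complete and subjects who stop early, so arms with different stopping rates would differ in that mix.

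**Working it through.** **1. Length of the two windows.** The inputs are Day 126 and follow-up at +30 days with a +7 day window (protocol Table 1, repeated in SAP section 1.2).

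- Completer, treatment period: 126 days.
- Completer, SAP window: 126 + 30 = 156 days to 126 + 37 = 163 days.
- Off-drug share of the SAP window: 30/156 = 19.2% to 37/163 = 22.7%.
- Lengthening relative to the treatment period: 30/126 = 23.8% to 37/126 = 29.4%.
- A subject who stops at day 28 (an illustration): 30/58 = 51.7% to 37/65 = 56.9% of the SAP window is off drug.

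These are scheduled values. The protocol text gives 30 days as a minimum, so an actual contact could be later.

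**2. Effect on the drug-placebo contrast.** The documents give no AE rates and no off-drug risk, so everything in this step is an assumption shown over a range. Onset hazards are constant. Let p0 and p1 be the 126-day incidences on placebo and drug, f the off-drug days, and h0 and h1 the daily hazards:

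- h = −ln(1 − p)/126
- placebo, SAP window: 1 − exp(−h0 × (126 + f))
- drug, SAP window: 1 − exp(−h1 × 126 − h_off × f)

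Three values of the drug arm's off-drug hazard h_off are used: h0 (risk returns to background), h1 (risk persists) and 2 × h1 (risk rises after stopping). The table gives risk differences in percentage points. Each range runs from f = 30 to f = 37.

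| Placebo v drug, 126 days | Treatment period | Returns to background | Persists | Doubles |
|---|---|---|---|---|
| 5% v 10% | 5.0 | 4.9 to 4.9 | 6.1 to 6.3 | 8.3 to 9.0 |
| 20% v 40% | 20.0 | 19.0 to 18.7 | 22.7 to 23.3 | 28.8 to 30.5 |
| 40% v 60% | 20.0 | 17.7 to 17.2 | 21.0 to 21.1 | 27.3 to 28.3 |
| 50% v 75% | 25.0 | 21.2 to 20.4 | 24.4 to 24.2 | 29.5 to 29.7 |

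Worked line for 20% v 40%, f = 30, return to background:

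- h0 = −ln(0.8)/126, so placebo is 1 − 0.8^(156/126) = 24.1%.
- Drug is 1 − 0.6 × 0.8^(30/126) = 43.1%.
- The difference is 19.0 points, and the risk ratio falls from 2.00 to 1.79.

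With persistence, drug is 1 − 0.6^(156/126) = 46.9%. The difference is 22.7 points, while the risk ratio slips to 1.94. The sign of the change therefore depends on the off-drug risk, on how common the event is, and on whether differences or ratios are read.

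**The case against.** The strongest reply is that the SAP window is reasonable in itself. Protocol section 7.1 wants AEs captured in post-treatment periods, and section 6.3.5 collects them for at least 30 days after stopping. Counting them is ordinary safety practice and can reveal delayed events. That stands: the fault is the unreconciled mismatch, not the inclusion.

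Several further points also stand.

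- The window is not unlimited. It ends at the follow-up contact, scheduled at 30 to 37 days.
- Section 9.2.5 attaches the treatment period to AE characteristics. Its sentence on incidence by system organ class carries no window, so the incidence definition rests on the synopsis and section 3.4.2.
- The protocol does not say when the Double-Blind Treatment Period ends for someone who stops drug early, so its own window is imprecise.
- AE summaries are descriptive, so no planned test is affected.
- SAP section 7 looks ahead to deviations from the SAP itself. It does not list differences from the protocol, so it cannot be read as a statement that there are none.

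A reader might infer that the longer window shrinks any drug-placebo difference. The documents do not support that, because they give no off-drug risk. Shrinkage follows if risk falls to background, but the difference can widen if risk persists or rises. Even under a return to background, the change in the difference is small for uncommon events (5.0 to 4.9 points at 5% v 10%).

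A reader might also infer that every TEAE table is affected alike. The table of events leading to discontinuation should gain little from events that start after the last dose. The related-event table is filtered by a causality rating that takes timing into account.

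**Conclusion.** The mismatch is in the text. As written, the SAP's TEAE tables do not give AE incidence within the Double-Blind Treatment Period, and no planned table does. The off-drug share is about 19% to 23% of a completer's window under the scheduled follow-up. It can exceed half for an early stopper.

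The effect on the comparison between arms has no fixed direction. In the 20% v 40% illustration it runs from 18.7 to 30.5 points against 20.0, depending entirely on the assumed off-drug hazard. These figures rest on constant hazards and assumed incidences, and show what could happen rather than what to expect.

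The uncertain direction is itself the reason to separate the periods. The point concerns safety reporting only and does not touch the sample size or the efficacy analysis.

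**What to change.** 1. Reconcile the protocol and SAP windows, and record in the SAP which window each AE summary uses.
2. In SAP section 3.3.7, state the end of the TEAE window relative to last dose, for both new and worsening events.
3. In SAP section 5.3.1 and the table list, add the overall TEAE summary and the SOC/PT summary restricted to the Double-Blind Treatment Period. State how that period ends for subjects who stop early. Flag events with post-treatment onset or show them separately.
4. Keep the full-window tables alongside. Do not make a last-dose cut-off the sole between-arm comparison: it shortens time at risk in any arm with more early stops and could hide toxicity there.

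No new data are needed. AE onset is already collected, and SAP section 3.3.7 already takes the final treatment day from the End of Study eCRF page. The cost is SAP wording, an on-treatment flag and a second set of AE tables.

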1.1.1.1 Berberine and Ursodeoxycholic Acid

Berberine is an isoquinoline alkaloid found in many different plants, with a long history of use in traditional Chinese medicine (Caliceti et al., 2016, Kumar et al., 2015). Berberine chloride (BBR·Cl) is an approved antiseptic drug in China, Japan, and Taiwan. In the United States (US) and Australia, BBR is widely used in various dietary supplements for a number of advertised health benefits and is grandfathered under the

Dietary Supplement Health and Education Act (DSHEA) in the US (Council for Responsible Nutrition 1998). The reported multi-spectrum activity of BBR, including effects on glucose and lipid metabolism, hepatic steatosis, oxidative stress, inflammation, and fibrosis suggests that BBR has the potential to treat NAFLD/NASH. Furthermore, clinical studies of BBR for the treatment of T2DM, hyperlipidemia, hypertension, and NAFLD have yielded favorable results (Cicero and Ertek 2009, Lan et al., 2015).

Ursodeoxycholic acid is a secondary bile acid produced by intestinal bacteria as a metabolic by-product, which is approved by the US Food and Drug Administration (FDA) for the non-surgical treatment of cholesterol gallstone dissolution (Actigall®, NDA 019594) and the treatment of primary biliary cirrhosis (PBC) (URSO 250® and URSO Forte®, NDA 020675). Similar to BBR, UDCA activity is reported to include anti-oxidative stress, anti-inflammatory, anti-apoptotic, and anti-fibrotic effects, as well as improvement in liver injury caused by microbial dysbiosis. In the clinical setting, favorable results were reported for UDCA combination therapy compared to UDCA monotherapy in the treatment of NASH (Xiang et al., 2013).

Based on the pharmacological properties and clinical evaluations of BBR and UDCA relative to NASH and conditions that are most commonly attributed to its development, BBR and UDCA may present as good "partners" for effectively treating this advanced liver disease. More information about the activity, safety, and efficacy of BBR and UDCA can be found in the HTD1801 Investigator's Brochure.

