1.2.2 Rationale for Dose and Duration

Ursodeoxycholic acid is approved by the US FDA at a dose of 13-15 mg/kg/day (URSO 250® and URSO FORTE®), or approximately 1 g/day for a 70 kg individual. Berberine is widely used in dietary supplements in the US at a recommended dose of 17-33 mg/kg/day, or approximately 1-2 g/day for a 70 kg individual. Furthermore, New Tantose A®, an over-the-counter combination including BBR (adult dose of 0.300 g/day) and UDCA (0.030 g/day), has been approved in Japan for acute diarrheal illness (New Tantose A®), while the therapeutic dosage in most of BBR's clinical experience is around 0.4-2.7 g/day orally for exposures up to 181 days (Cicero and Ertek 2009, Lan et al., 2015). As shown in Table 3, the UDCA and BBR content of HTD1801 are comparable to doses associated with clinical safety.

Table 3. Comparison of HTD1801 Clinical Dose with FDA Approved UDCA Dose and Clinical BBR Dose

| Compound | FDA Approved Clinical Dose (UDCA) / Dose Used in Clinical Experience (BBR) | HTD1801 Clinical Dose (29 mg/kg/day; 2,000 mg/day) ^{a,d} |
|-------------------|--|--|
| UDCA ^a | 13-15 mg/kg/day (910-1,050 mg/day) ^b | 15 mg/kg/day (1,078 mg/day) |
| BBR ^a | 6-38 mg/kg/day (400-2,700 mg/day) ^c | 15 mg/kg/day (1,022 mg/day) |

^a mg/kg doses calculated assuming a 70 kg adult.

Furthermore, data from a first-in-human, single ascending dose study of HTD1801 in healthy subjects (Protocol HTD1801.PCT002) demonstrated dose proportionality for

^b Safety at doses up to 25 mg/kg/day is supported by the published literature for PBC patients (Angulo et al., 1999).

^c Therapeutic dosage in most of BBR's clinical experience (Cicero and Ertek 2009, Lan et al., 2015).

d HTD1801 dose of 2,000 mg/day is equivalent to 1,022 mg/day BBR and 1,078 mg/day UDCA.

UDCA and BBR exposure parameters at orally administered HTD1801 doses of 0.5-4.0 g/day. Single doses of HTD1801 were also safe and well tolerated.

Lastly, recent Phase 2 POC studies in NASH (Harrison et al., 2018, Madrigal Pharmaceuticals 2018) show clinically meaningful absolute and relative reductions in LFC assessed by MRI-PDFF over 12-week treatment periods. An 18-week HTD1801 treatment period is therefore adequate to assess the study's primary endpoint and to maximize collection of exposure and safety related data.

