4.0 STUDY DRUGS AND DOSAGES

4.1 IDENTIFICATION AND DESCRIPTION OF INVESTIGATIONAL PRODUCT

4.1.1 Investigational Product

The HTD1801 drug substance, berberine ursodeoxycholate, is the salt formed between BBR and UDCA with a stoichiometry of 1:1. The HTD1801 drug product is a film-coated tablet containing 250 mg of berberine ursodeoxycholate. HTD1801 is expected to dissociate into BBR salt and UDCA after oral administration.

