Total bile acids, C4, and FGF19 are biomarkers that will be utilized in this study to assess bile acid homeostasis. Factors implicated in the pathogenesis of NASH, such as obesity or increased BMI, insulin resistance, and elevated AST and ALT serum concentrations to the dysregulation and increase of serum bile acids. Likewise, elevations in serum C4, an indicator of bile acid synthesis in vivo, have been observed in NASH patients. Conversely, reduced serum concentrations of FGF19, which inhibits the rate-limiting enzyme CYP7A1 to regulate bile acid synthesis, have also been observed in NASH patients (Zhang and Deng 2018). Furthermore, the results of a recent study of BBR administered to wild type and farnesoid X receptor (FXR)

knockout mice suggest that BBR may exert its lipid-lowering effect by modulating bile acid turnover and activating the FXR-FGF19 signaling pathway (Sun et al., 2017).

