Total bile acid is calculated as the sum of all bile acid measurements and metabolites at a visit for a given subject.

Total Primary Bile Acid

Total primary bile acid is calculated as the sum of cholic acid, chenodeoxycholic acid, glycocholic acid, glycochenodeoxycholic acid, taurocholic acid, and taurochenodeoxycholic acid at a visit for a given subject.

Total Secondary Bile Acid

Total secondary bile acid is calculated as the sum of deoxycholic acid, lithocholic acid, glycodeoxycholic acid, glycolithocholic acid, taurodeoxycholic acid, and tauroolithocholic acid at a visit for a given subject.

Total Ursodeoxycholic Acid

Total ursodeoxycholic acid is calculated as the sum of ursodeoxycholic acid, glyoursodeoxycholic acid, and tauroolithocholic acid at a visit for a given subject.

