5.2.5. Secondary Efficacy Analysis

Change and percent change from Baseline in LFC will be summarized by treatment group and study visit. Differences in percent change from Baseline in LFC will be assessed by analysis of covariance that includes the effects of treatment group, Baseline LFC, and Baseline ALT, comparing each active treatment group to placebo, as well as a comparison of the combined active treatment groups vs. placebo. A figure summarizing LS means of percent change from Baseline at Week 18 by treatment group will also be generated.

Changes from Baseline to Week 18 in the laboratory assessments listed as secondary efficacy endpoints (fasting glucose, HbA1c, HOMA-IR, LDL-c, serum triglycerides, HDL-c, AST, ALT,

Pro-C3, ELF, total bile acids, C4, FGF19) will be assessed by analysis of covariance that includes the effects of treatment group and Baseline value, comparing each active treatment group to placebo. For these analyses, missing Week 18 values will be imputed using the methods described in section 3.3.4. For HbA1c, this model will also be run without imputed values. For all bile acid analyses other than total bile acid, all analyses will be performed without imputation. Figures summarizing change from Baseline over time by treatment group will also be generated for these laboratory assessments. The number and percentage of subjects who achieve $\geq 30\%$ relative reduction in LFC as measured by MRI-PDFF from Baseline to Week 18 will be summarized by treatment group and study visit. The proportion of subjects who achieve $\geq 30\%$ relative reduction in LFC as measured by MRI-PDFF from Baseline to Week 18 will be analyzed by logistic regression that includes the effects of treatment group, Baseline LFC, and Baseline ALT. A figure summarizing the proportion of subjects achieving $\geq 30\%$ relative reduction in LFC as measured by MRI-PDFF from Baseline to Week 18 by treatment group will also be generated.

The number and percentage of subjects who normalize LFC to $< 5\%$ as measured by MRI-PDFF at Week 18 will be summarized by treatment group and study visit. The proportion of subjects who normalize LFC to $< 5\%$ as measured by MRI-PDFF at Week 18 will be analyzed by logistic regression that includes the effects of treatment group, Baseline LFC, and Baseline ALT. A figure summarizing the proportion of subjects who normalize LFC to $< 5\%$ at Week 18 by treatment group will also be generated.

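### Total bile acids, one of three named homeostasis biomarkers, counts the UDCA in the study drug, and no UDCA-free total is prespecified

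*SAP*

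**What the plan says.** Protocol 6.2.2 names the measures for the bile acid objective: "Total bile acids, C4, and FGF19 are biomarkers that will be utilized in this study to assess bile acid homeostasis". The same section links factors implicated in NASH, such as obesity and insulin resistance, "to the dysregulation and increase of serum bile acids".

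SAP 3.3.7 defines the first measure: "Total bile acid is calculated as the sum of all bile acid measurements and metabolites at a visit for a given subject". UDCA is not excluded.

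On the drug, Protocol 4.1.1 states: "The HTD1801 drug substance, berberine ursodeoxycholate, is the salt formed between BBR and UDCA with a stoichiometry of 1:1". It adds that "HTD1801 is expected to dissociate into BBR salt and UDCA after oral administration". The notes to Protocol Table 3 (section 1.2.2) give the content: "HTD1801 dose of 2,000 mg/day is equivalent to 1,022 mg/day BBR and 1,078 mg/day UDCA". Protocol 1.1.1.1 places UDCA among the bile acids: "Ursodeoxycholic acid is a secondary bile acid produced by intestinal bacteria as a metabolic by-product".

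SAP 3.3.7 also defines sub-totals for primary, secondary and ursodeoxycholic acids. SAP 5.2.4 lists each as a secondary endpoint, and each has its own table (14.2.2.11.2 to 14.2.2.11.4). SAP 5.2.5 names total bile acids, C4 and FGF19 among the variables for ANCOVA against placebo; the sub-totals are not named there. The same section adds: "For all bile acid analyses other than total bile acid, all analyses will be performed without imputation". Figure 14.2.3.10 shows the overall total. No sub-total has a figure.

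**The concern.** The total contains part of what subjects swallow. UDCA absorbed from the tablets is added in the active arms only, after baseline, and the amount taken differs twofold between the two doses. An ANCOVA of each active arm against placebo counts that addition as a treatment effect.

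Two misreadings follow. A dose-ordered rise could be taken as a change in bile acid homeostasis when the endogenous pool has not moved. Because the protocol associates raised serum bile acids with NASH, that rise would look like worsening. Conversely, a real fall in endogenous bile acids could be cancelled or reversed in the total. At stake is the reading of one of the three biomarkers behind secondary objective 5.

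**Working it through.** **Inputs from the documents.** Protocol Table 3 and its notes: 2,000 mg/day HTD1801, equivalent to 1,078 mg UDCA and 1,022 mg berberine, for a 70 kg adult. Arms: 1,000 mg BID, 500 mg BID, placebo.

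**Step 1. Reproduce Table 3.** 1,078/70 = 15.4 mg/kg/day and 1,022/70 = 14.6 mg/kg/day. Both are shown as 15, so the table reproduces.

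**Step 2. UDCA share of the dose.** 1,078/2,000 = 53.9%. The two components sum to 1,078 + 1,022 = 2,100 mg rather than 2,000 mg, and the documents do not explain the basis. On that denominator the share is 1,078/2,100 = 51.3%. Either way it is about half.

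**Step 3. Daily UDCA by arm.** High dose 1,078 mg; low dose 1,078/2 = 539 mg; placebo 0.

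**Step 4. Effect on the total.** The documents give no serum bile acid levels, so this step rests on an assumed range. Let the baseline total be 1, with negligible UDCA. Let e be the true relative change in the non-UDCA acids, and s the share of the on-treatment total that is drug-derived UDCA. The on-treatment total is then (1 + e)/(1 − s), and its apparent change is

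(1 + e)/(1 − s) − 1.

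| s (assumed) | 10% | 20% | 30% | 40% | 50% | 60% |
|---|---|---|---|---|---|---|
| e = 0 | +11% | +25% | +43% | +67% | +100% | +150% |
| e = −30% | −22% | −12.5% | 0% | +17% | +40% | +75% |

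Example: at s = 0.4 and e = −0.3, 0.7/0.6 = 1.167, a 17% rise. An endogenous fall equal to s is cancelled exactly.

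The definition of s matters. Suppose instead that the drug load is fixed at the amount that makes up 40% of the total when the pool is unchanged (0.4/0.6 = 0.667). A 30% endogenous fall then gives 0.7 + 0.667 = 1.367, a 37% rise, but UDCA is now 0.667/1.367 = 49% of the total. The table uses the share actually present on treatment.

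**Step 5. Do the sub-totals separate the two?** The primary list holds cholic and chenodeoxycholic acid with their glycine and taurine conjugates. The secondary list holds deoxycholic and lithocholic acid with theirs. Neither contains UDCA or a UDCA conjugate, although the protocol calls UDCA a secondary bile acid. Their sum would return e for the listed acids.

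Subtracting the UDCA sub-total from the overall total would not be a clean alternative. As written, that sub-total contains a taurolithocholic acid, which is already counted as secondary, and no taurine conjugate of UDCA.

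**The case against.** The strongest reply is that the SAP already handles most of this. The primary and secondary sub-totals are listed endpoints with their own tables and contain no UDCA, so a fall in those acids would be visible there. C4 and FGF19 are not bile acid sums, so the added UDCA does not enter them arithmetically. This stands. A reader might infer that total bile acids measures dosing instead of homeostasis, or that objective 5 cannot be answered. The documents do not support that: the total is a mixture, two other named biomarkers remain, and Protocol 6.2.2 itself raises the possibility that berberine modulates bile acid turnover.

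A reader might also infer that only the overall total will be tested. That is not established. SAP 5.2.5 applies ANCOVA to laboratory assessments listed as secondary endpoints, and its bracketed list also omits GGT, which is a listed endpoint with its own table. The list is unclear rather than exclusive.

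Finally, nothing shows that drug-derived UDCA dominates serum. Samples are taken after a fast of at least 8 hours (Protocol 5.1) and tablets are taken with food (4.2), so the sampled share is unknown. Protocol 1.2.2 does report dose-proportional UDCA exposure at 0.5 to 4.0 g/day. That supports a dose-related contribution, but it comes from single doses in healthy subjects.

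The reply does not remove the gap. The confounded sum is the one with the named ANCOVA, the imputation and the figure, and no combined UDCA-free sum is planned.

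**Conclusion.** The point holds as a confounding problem in one of three homeostasis biomarkers. By definition, the active-versus-placebo difference in total bile acids includes study drug, so read alone it cannot show an endogenous change.

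The direction of the distortion follows from the documents; its size does not. The range of +11% to +150% with no endogenous change rests on an assumed UDCA share of 10% to 60%, with negligible UDCA at baseline. Exclusion criterion 22 gives that last assumption some support, since it bars UDCA used as an unapproved NASH treatment within 30 days before Screening.

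This is a secondary endpoint in a proof-of-concept trial, and the interim decision rules use liver fat only. It is a cheap improvement to interpretation and does not threaten the primary result.

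**What to change.** - **Add a UDCA-free total** in SAP 3.3.7, 5.2.4 and 5.2.5, defined by naming the primary and secondary acids already listed in 3.3.7. Naming them matters because the protocol classes UDCA as secondary. Make it the bile acid sum used to interpret objective 5.
- **Give it the same treatment as the overall total:** the ANCOVA, the imputation and a figure. The sentence in 5.2.5 that limits imputation to total bile acid needs a matching exception.
- **Keep the overall total,** since the protocol names it. State in the SAP and in table and figure footnotes that it and the UDCA sub-total include study drug.
- **Check and correct the UDCA sub-total,** which lists a taurolithocholic acid and no taurine conjugate of UDCA. Until then, do not use it for subtraction.
- **Clarify in 5.2.5** whether the sub-totals are tested by ANCOVA.

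The cost is SAP wording and one more secondary analysis, using acids that the existing sub-totals already require. The protocol endpoint is not replaced. The drawback is that the small amount of endogenous UDCA is left out, in all arms alike, as are any measured acids outside the two lists. The documents do not say whether drug-derived UDCA is converted into any listed acid, so the new total should be described as free of UDCA, not of every drug effect on composition.
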